Patient Inclusion / Exclusion Criteria	
Inclusion criteria
 
 1. Signed informed consent available 2. Male or female patients ≥ 18 years of age 3. Patients with chronic intestinal failure receiving HPN including lipids in whom the parenteral macronutrients have not been changed by more than 10% for at least 3 months 4. Patients receiving ≥ 3.0 g lipids/kg body weight per week 
Exclusion criteria
 
 1. Persistent high total bilirubin values in medical history of last 6 months ($> 40 \mu\text{mol/l}$) 2. Patients in whom PN was interrupted for longer than 4 continuous weeks in the preceding 6 months 3. Patients with history of cancer and anti-cancer treatment within the last 2 years 4. Hypersensitivity to egg, fish, peanut or soya-bean protein or to any of the active substances or excipients 5. Patients treated in the past or currently with Teduglutide 6. Contraindications to investigational products (if available from medical records) including: 
 • Severe hyperlipidemia, including severe hypertriglyceridaemia (≥ 1000 mg/dl or 11.4 mmol/l)

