Visit Schedule	
Screening
 
 ▪ Preferably during a regular patient monitoring visit ▪ Patient information and signature of informed consent form (patient information sheet might be provided to the patient prior the visit) ▪ Verification of inclusion and exclusion criteria ▪ Pregnancy test (urine dipstick), if applicable 
Randomization
 
 ▪ After check of all inclusion and exclusion criteria the patient will be randomized. 
Baseline
 
The baseline assessment is performed after randomization on the day of screening.
 
Documentation of:
 
 ▪ Demographic data ▪ Anamnesis ▪ Physical examination 
Assessment of safety, efficacy and other variables (blood samples will be taken the earliest 3 hours after the last PN infusion):
 
 ▪ Vital signs ▪ Laboratory values from routine blood samples 
 • Hepatic function (incl. blood samples for central laboratory analyses of primary variable) • Blood count and coagulation • Other biochemical parameters ▪ Blood samples for central laboratory analyses of fatty acid pattern in RBCs and plasma ▪ QoL ▪ Concomitant medication ▪ AEs continuously from start of study 
The patient will be provided with a patient diary for documentation of IP

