	
 ▪ Body weight ▪ Laboratory results 
 • Hepatic function (incl. blood samples for central laboratory analyses of primary variable) • Blood count and coagulation • Other blood biochemistry parameters ▪ Blood samples for central laboratory analyses of fatty acid pattern in RBCs and plasma ▪ QoL ▪ Treatment compliance will be documented in the eCRF on the basis of patient diary entries ▪ Concomitant medication ▪ AEs 
Patient diary will be collected and data entered in the eCRF
 
Visit 2 is the final study visit for the patient and study termination page of the eCRF will be completed.
 
After this final visit no IP must be administered. The PN treatment will continue according to the decision of the physician with a regularly used lipid emulsion.

Duration of Study per Patient	
Start of study: with randomization
 
Treatment period (infusion of IP):
 
 ▪ Start of IP infusion within one week after randomization ▪ Treatment with IP is projected for a period of 8 weeks on average and will not end before visit 2 
End of study: Final visit (study visit 2)

Study Schedule	
Planned start: Q1 / 2018
 
Planned recruitment time: 5.5 years
 
Planned last patient out: Q2 / 2023

Statistical Methods	
Two sample t-test for mean difference assuming equal variances (testing non-inferiority)
 
Descriptive statistics including methods for the comparison of two groups (t-test, U test, χ^2 test)

Randomization / Blinding	
Patients will be assigned at a 1:1 ratio to receive either Lipidem or Lipofundin MCT. The allocation to one of the two treatment groups will be performed by permuted block randomization with stratification for study site.
 
The study is double-blind.

Data and Safety Monitoring Board (DSMB)	
A DSMB will not be appointed.

Statistical Analysis and Evaluation

Statistical methods

All programming of tables, figures, listings and statistical analyses will be performed using SAS® version 9.4 (or higher). The planned statistics will be performed in accordance with the principles outlined by the guideline ICH E9.

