The primary endpoint of the study is the change of liver function parameters defined as the sum of the N(0,1)-transformed differences from baseline in ALT, AST, and bilirubin after 8 weeks of treatment. It is the aim to demonstrate non-inferiority of the primary endpoint with respect to 'deterioration in liver function' using the non-inferiority margin $\delta=1.151$. This margin was derived as ' $\sigma/2$ ' from a previous study on the use of lipid emulsions in HPN patients which provided a standard deviation of 2.3029 for the specified endpoint. The non-inferiority will be shown using the two-sample t-tests for mean differences assuming equal variances under the following conditions:

- distribution : normal
- method : exact
- number of sides: 1
- alpha : 0.025
- mean difference : 1.151 (= non-inferiority margin δ).

The primary analysis will be performed for the Valid case set (FAS for sensitivity). No imputation will be performed.

Thus, the t-test will compare the (one-sided) null hypothesis

- $H_0: \Delta_T \geq \Delta_S + \delta$

against the alternative hypothesis

- $H_1: \Delta_T < \Delta_S + \delta$

on the level of 0.025, where Δ_T and Δ_S represent the increase of the primary endpoint upon T=test and S=standard. Non-inferiority (with non-inferiority margin $\delta=1.151$) can be concluded, if the VCAS analysis yields an upper limit of the two-sided 95% confidence interval (or one-sided 97.5% confidence interval) for the treatment contrast of the primary endpoint lower than 1.151 and if this result is confirmed by the corresponding FAS analysis.

Superiority of T vs S, i.e. $H_0: \Delta_T \geq \Delta_S$ vs. $H_1: \Delta_T < \Delta_S$, is demonstrated simultaneously, if the upper limit of the confidence interval is below zero for both the FAS analysis and the VCAS analysis.

Given the non-inferiority of T vs. S, the following procedure will be performed subsequently:

- breakdown of the multiple primary endpoint to its components ALT, AST, and bilirubin with unchanged level (Lehmacher *et al.*, 1991).

Further methods are descriptive statistics including standard procedures for the comparison of two groups (t-test, U test, χ^2 test).

Interim Analysis

No interim analyses are planned.

Level of significance and power

The primary endpoint will be tested one-sided with an significance level of $\alpha=0.025$.

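### The primary t-test is valid but ignores baseline ALT, AST and bilirubin and the site stratum; a prespecified ANCOVA would usually narrow the non-inferiority interval at little cost

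*Combined protocol and SAP*

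**What the plan says.** Under Statistical Analysis and Evaluation, Statistical methods: "The non-inferiority will be shown using the two-sample t-tests for mean differences assuming equal variances under the following conditions". The Statistical Methods row of the Study Overview names the same equal-variance test. The endpoint is the sum of the standardised changes in ALT, AST and bilirubin from baseline to visit 2, so baseline enters only by subtraction. Non-inferiority is concluded if the upper 95% limit lies below 1.151 in the valid case set and "if this result is confirmed by the corresponding FAS analysis".

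The step that follows is a "breakdown of the multiple primary endpoint to its components ALT, AST, and bilirubin with unchanged level", again without covariates. The remaining methods are descriptive statistics and t, U and chi-square tests.

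The variables an adjusted model would need are already there. The baseline visit lists "Hepatic function (incl. blood samples for central laboratory analyses of primary variable", and the Randomization / Blinding row says: "The allocation to one of the two treatment groups will be performed by permuted block randomization with stratification for study site".

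**The concern.** A change score assumes that one unit of baseline predicts exactly one unit at follow-up. When the true slope is not 1, the change remains correlated with baseline, and a two-sample t-test leaves that explainable variance in the error term. The stratification factor is left out as well.

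The verdict turns on one upper confidence limit that must clear 1.151 in two analysis sets, and the same limit decides superiority. A wider interval raises the chance of missing a true non-inferiority. In the realised trial, a chance baseline difference between arms also shifts the contrast, in the opposite direction when the slope is below 1. The exposure is greatest if fewer than 80 per arm are evaluable, which is possible because missing values are not imputed.

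**Working it through.** **Inputs from the plan.** SD of the summed endpoint σ = 2.3029 (the earlier study "provided a standard deviation of 2.3029 for the specified endpoint"); margin δ = 1.151; one-sided α = 0.025; target power 80%; 80 per arm; up to 15 sites. **Assumed:** true difference 0; r, the baseline to visit 2 correlation; k, visit 2 SD divided by baseline SD.

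**1. The plan's own figures.** σ/2 = 2.3029/2 = 1.15145, which matches the margin. Power of the t-test is 1 − F(t(0.975, 2n−2)), where F is the noncentral t distribution with 2n−2 df and noncentrality δ/(σ√(2/n)):
- n = 63: 79.5%; n = 64: 80.1%; n = 80: 88.1%.
- Half-width t × σ × √(2/n): 1.975 × 2.3029 × 0.1581 = 0.719 at 80 per arm; 1.979 × 2.3029 × 0.1768 = 0.806 at 64.

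The stated inputs therefore need 64 per arm. 64/0.80 = 80, but no dropout rate is stated, so 64 is an inferred figure.

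**2. Variance that baseline can remove.** With baseline SD 1 and visit 2 SD k, the change has variance 1 + k² − 2rk and covariance rk − 1 with baseline. The removable share is

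R² = (1 − rk)² / (1 + k² − 2rk).

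At k = 1 this is (1 − r)/2. It is zero only at k = 1/r.

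**3. Analytic check, three baselines only, k = 1.** Replace σ by σ√(1 − R²) × √(1 + 3/(2n − 6)) and use 2n − 5 df. For r = 0.5, 0.7, 0.8 and 0.9, power is 94.9%, 92.1%, 90.7% and 89.1% at 80 per arm, and about 89%, 85%, 83% and 81% at 64.

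**4. Simulation, three baselines plus site.** 8,000 trials per cell (Monte Carlo SE about 0.35 points); normal components with common correlation 0.384, from (2.3029²/3 − 1)/2, so that the sum has SD 2.3029; 15 unequal sites; blocks of 4 (assumed); sites with fewer than 4 patients pooled. With k = 1 and no site variance, t-test → ANCOVA:

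| r | R² | Power, 80/arm | Half-width, 80/arm | Power, 64/arm |
|---|---|---|---|---|
| 0.5 | 25% | 87.7 → 94.1% | 0.719 → 0.633 | 79.6 → 88.4% |
| 0.7 | 15% | 88.5 → 91.7% | 0.719 → 0.674 | 80.5 → 84.7% |
| 0.8 | 10% | 88.7 → 90.4% | 0.719 → 0.693 | 80.3 → 82.8% |
| 0.9 | 5% | 88.5 → 89.2% | 0.719 → 0.711 | 79.7 → 79.9% |
| 0.95 | 2.5% | 88.0 → 88.0% | 0.719 → 0.721 | 79.5 → 79.1% |

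**5. Unequal SDs, no site variance.**

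| r, k | R² | Power, 80/arm | Power, 64/arm |
|---|---|---|---|
| 0.8, 0.9 | 21.2% | 88.3 → 94.0% | 80.3 → 87.3% |
| 0.8, 1.1 | 3.2% | 88.3 → 88.3% | 80.2 → 79.3% |
| 0.8, 1.25 | 0% | 88.3 → 87.1% | 80.2 → 78.6% |
| 0.8, 1.4 | 2.0% | 88.3 → 88.6% | not run |
| 0.5, 1.25 | 10.7% | 88.1 → 90.7% | not run |
| 0.7, 1.2 | 3.4% | 87.6 → 87.7% | not run |

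**6. Site holding an assumed 5% of variance, k = 1.** For r = 0.5, 0.8, 0.9 and 0.95:
- 80 per arm: 88.6 → 95.6%, 89.2 → 91.5%, 88.1 → 89.4%, 88.1 → 88.8%.
- 64 per arm: 80.4 → 90.4%, 80.9 → 84.8%, 80.5 → 82.3%, 80.5 → 81.2%.

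**7. Validity.** Simulated type I error at a true difference of 1.151 (16,000 trials per cell) is 2.4–2.7% for the t-test and 2.5–2.6% for ANCOVA. With 5% site variance it is 2.1–2.2% and 2.4–2.6%. Neither test is materially inflated.

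**8. Baseline imbalance.** A two-SE imbalance shifts the unadjusted contrast by σ × (1 − rk)/√(1 + k² − 2rk) × 2√(2/n). At 80 per arm and k = 1:
- r = 0.5: 2.3029 × 0.5 × 0.3162 = 0.364, or 0.364/1.151 = 32% of the margin.
- r = 0.8: 0.230.
- r = 0.9: 0.163, or 14% of the margin.

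At r = 0.8 the shift falls to 0.130 at k = 1.1 and to 0 at k = 1.25.

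**The case against.** The strongest reply is that nothing is wrong: endpoint, hypotheses, sample-size settings and test all use the same unadjusted contrast, type I error is controlled, and 80 per arm already exceeds the 80% target. That is correct, and it is why this is an improvement and not an error.

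The gain rests on r and k, which the documents do not give. Of the nine simulated cells with k ≠ 1, only three show a gain beyond noise. The plan also has features that could favour small gains: parenteral macronutrients must have been stable for at least 3 months, visits are matched to baseline timing, and the exclusion of "Persistent high total bilirubin values in medical history of last 6 months" acts at entry but not at visit 2, which could push k above 1 for bilirubin. This stands as a limit on the size of the gain.

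The loss may exceed 1 to 2 points. Two smaller runs of 4,000 trials at 64 per arm gave 79.7 → 77.4% (r = 0.8, k = 1.25) and 81.4 → 78.4% (nothing prognostic, small sites not pooled). Each of those power figures has a Monte Carlo SE of about √(0.8 × 0.2/4000) = 0.6 points, so they are compatible with a loss near 2 points.

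Site adds little: about 0 to 0.5 points over the baselines when it holds 5% of variance, and a cost of about 1.6 points when nothing is prognostic. This stands too; most of the gain comes from the baselines. Skewed components were not simulated.

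Two replies do not carry. The interval does cover chance imbalance on average over repeated trials, but that does not remove the shift in the trial actually run. Adjusting each component only for its own baseline means that the component contrasts no longer sum to the global one, but nothing in the planned breakdown requires that they do.

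**Conclusion.** The point holds as an efficiency improvement; the t-test itself is valid. With equal SDs and no site differences, ANCOVA adds about 1 to 6 points of power at 80 per arm for r from 0.9 down to 0.5, and about 2.5 to 9 points at 64 per arm for r from 0.8 down to 0.5. The half-width at 80 per arm falls from 0.72 to between 0.71 and 0.63. At r of about 0.95, or with k near 1/r, there is no gain or a loss of about 1 to 2 points if sites do not differ.

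These sizes assume normal components, a true difference of 0, and values of r and k that the documents do not supply. The need is greatest if the valid case set falls well below 80 per arm, since power at the full number is already about 88%.

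**What to change.** Before unblinding, change the Statistical Methods row of the Study Overview and the Statistical methods section together:

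- Primary analysis in both the valid case set and the FAS: ANCOVA of the same summed standardised change on treatment, baseline ALT, baseline AST, baseline bilirubin and site, with small sites pooled by a rule fixed in advance.
- State that the standardising SDs are those of the unadjusted changes, so that the endpoint scale and the margin of 1.151 keep their meaning.
- In the component breakdown, adjust each component for its own baseline and site.
- Keep one-sided α = 0.025 and the 95% confidence interval rule, and keep the two-sample t-test as a sensitivity analysis.

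The cost is wording in two places and a pooling rule, with no added patients, samples or procedures. The section on missing data and outliers already provides for a blinded review before database lock that can lead to an SAP update. The change must be dated before unblinding; an adjusted model chosen afterwards would be open to challenge. The statistical downside is the possible loss of about 1 to 2 points of power described above.

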Tests of secondary variables will be carried out in the area of exploratory data analysis. Therefore, corresponding p-values are to be regarded as exploratory ones and no adjustments for multiple testing will be made.

Sample size calculation is performed with a power of 80%.

Statistical hypotheses

The higher 'deterioration in liver function' is indicated by a higher sum of the $N(0,1)$ -standardized changes from baseline to visit 2 in ALT, AST and bilirubin. Therefore, the hypotheses specified before will show – in case of significance – that the potential deterioration in liver function is not relevantly higher upon T than upon S.

Data handling

All data will be listed. Whenever applicable all tables, figures and listings will identify patients using the patient identification (ID) and time of evaluation. For data collected prior to randomization, patients will appear in the listings with the treatment to which they were subsequently allocated.

The actual population presented in a table/figure/listing will be mentioned in the headings.

Tables and listings will be produced in accordance with the principles outlined by the ICH E3 guideline.

Handling missing data and outliers

Every effort will be made to collect all data points in the study. The amount of missing data will be minimized by appropriate management of the randomized, prospective, trial, proper screening of subjects, and training of participating investigators and other authorized staff (e.g. nurses), monitors and study co-coordinator. Since all patients who are randomized will be included in the primary analysis, in those instances where data are missing, missing values will not be imputed.

Prior to database lock a blinded data review meeting will be held to identify remaining data issues, review listings/graphs specifically created for the data review meeting, to assess the impact of protocol violations on the interpretation of data and to trigger last database corrections or an SAP update as applicable.

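### Does the follow-on step for ALT, AST and bilirubin need its own written margin and testing rules?

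*Combined protocol and SAP*

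**What the plan says.** The section Statistical Analysis and Evaluation, under Statistical methods, sets out the composite test in full: null and alternative hypotheses, one-sided alpha 0.025, and a margin of 1.151. The margin is half the standard deviation from an earlier study, "which provided a standard deviation of 2.3029 for the specified endpoint". The two deltas in the hypotheses "represent the increase of the primary endpoint upon T=test and S=standard". Non-inferiority is concluded if the upper confidence limit in the Valid case set lies below 1.151 "and if this result is confirmed by the corresponding FAS analysis".

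The marker step is one bullet. It opens with "Given the non-inferiority of T vs. S, the following procedure will be performed subsequently" and then gives "breakdown of the multiple primary endpoint to its components ALT, AST, and bilirubin with unchanged level", followed by a 1991 reference.

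Two other places bear on it. The Study Overview lists bilirubin, ALT and AST among the secondary hepatic safety variables. Under Level of significance and power the plan says "Tests of secondary variables will be carried out in the area of exploratory data analysis", so that "corresponding p-values are to be regarded as exploratory ones and no adjustments for multiple testing will be made". Finally, the section on missing data and outliers schedules a blinded data review before database lock, which may lead to a revised SAP.

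**The concern.** The contrast within one section is striking. The composite has every element written down; the markers have an entry condition, a level and a citation. Because the deltas are defined for the composite, its margin does not transfer to a single marker. A methods paper from 1991 cannot supply a margin for this trial either, so a programmer would have to choose one. The status could also be read two ways: the bullet keeps the primary level, while the same three markers appear in a list whose tests are exploratory.

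The stake is the primary safety objective. A sum can hide a single marker: if one is 0.5 SD worse and the other two are each 0.25 SD better, the true composite difference is 0.5 − 0.25 − 0.25 = 0, and the composite passes at full power. The marker step is the only place where each liver marker is tested at the primary level. A margin picked after unblinding, or marker tests without a pairwise stage, could turn an uncertain result into a claim.

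**Working it through.** **Inputs from the plan.** SD of the composite 2.3029; margin 1.151; one-sided alpha 0.025; power 80%; 80 patients per group.

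**Assumptions.** Each standardised marker has SD 1. Correlations are either all equal or 0.8, 0.176, 0.176, both chosen to give the composite SD of 2.3029. One analysis set is used, so FAS confirmation is not modelled. Simulation figures rest on 400,000 trials per setting unless noted.

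**1. The plan's own figures.** 2.3029 / 2 = 1.15145, so the margin reproduces. With 64 per arm the standard error is 2.3029 × √(2/64) = 0.407 and the noncentrality is 1.151 / 0.407 = 2.83; the exact t-test has 80.1% power. With 80 per arm it is 2.3029 × √(2/80) = 0.364, noncentrality 3.16, power 88.1%. The total of 160 equals 128 / 0.8, which fits 20% dropout; the visible text states no dropout rate.

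**2. Implied correlation.** The variance of a sum of three unit-variance markers is 3 + 6r, so r = (2.3029² − 3) / 6 = (5.303 − 3) / 6 = 0.384.

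**3. Candidate marker margins.**
- The plan's half-SD rule applied to one marker: 1 / 2 = 0.5.
- One third of the composite margin: 1.151 / 3 = 0.384. No passage divides the margin this way.
- The composite margin carried over unchanged: 1.151, or 1.15 SD of one marker, which is not half an SD of anything tested.

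Only 0.5 follows a rule that the plan uses. It also fits the entry condition: 3 × 0.5 = 1.5 exceeds 1.151, so if all three markers were at their margins the composite test would already limit false claims to 2.5%. A marker's stand-alone power is then 80% (64 per arm) or 88% (80 per arm), the same as the composite's, against 58% or 67% at 0.384.

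**4. How far the choice matters.** Trials that pass the composite, no true differences, markers tested directly:

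| | 64 per arm | 80 per arm |
|---|---|---|
| At least one verdict differs, 0.384 vs 0.5 | 48–49% | 43–44% |
| All three pass, margin 0.384 | 36–38% | 46–47% |
| All three pass, margin 0.5 | 73–75% | 82–84% |

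For a given marker the verdict differs in 19–22% across both sizes. The larger figure comes from counting a change in any of three markers.

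**5. The hidden-harm example.** One marker +0.5 SD, two at −0.25 SD. Among composite passes, the worse marker passes its own test in about 0.4–0.6% (margin 0.384) or 2.8–3.2% (margin 0.5). Refusal is therefore at least 100 − 3.2 = 96.8% either way. An ordinary two-group t-test, already planned as a descriptive method, shows that marker as significantly worse in about 75% of those trials at 64 per arm and 86–87% at 80.

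**6. Multiplicity.** With two markers at the margin and direct testing after the composite, the chance of a false marker claim is 2.7–2.9% (margin 0.5) or 3.7–4.2% (0.384) with the third unchanged, and 3.9–4.9% with the third 0.5–1.0 SD better. With pair tests at the sum of the two margins it is 1.7–2.5%. The excess arises only if the cited procedure has no pairwise stage, which the documents do not settle.

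**7. The text, side by side.** Type: entry is through non-inferiority, the Statistical Methods row of the Study Overview names non-inferiority for the t-test, and the Statistical hypotheses section speaks of deterioration that is not relevantly greater. Analysis set: the bullet breaks down the primary endpoint, whose analysis is set for the Valid case set with FAS confirmation. Status: the exploratory label covers tests of secondary variables; the marker step is a separate, gated part of the primary analysis. A marker can appear in both places without contradiction.

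**The case for a change.** The strongest case for a change is that a marker margin is not written anywhere, and reading one off the half-SD rule is an inference. Where the true differences are null, the two margins considered give noticeably different results, and all-three success roughly doubles at 64 per arm. If the step were meant as superiority, no margin would be needed, but direct testing without pair tests would give a familywise error of about 6.5% (200,000 simulated trials, correlation 0.384). Writing the rules down would cost almost nothing.

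Part of this stands. The margin and the status are not spelled out, and the simulation figures are right under their assumptions. The rest is weaker. The superiority reading runs against the entry condition and the wording of the hypotheses. The error figures require the cited procedure to lack a stage it may well contain. The rival margin of 0.384 is not derived anywhere in the plan. The case that would matter to patients, a marker truly worse by half an SD, is refused under both margins. Nothing in the plan suggests that the margin would be set after unblinding; the blinded review before database lock is the natural point to settle such details. The missing-data section also says that all randomised patients enter the primary analysis, which sits awkwardly with the Valid case set, but that concerns the primary analysis as a whole and not this step.

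**Conclusion.** No change to the plan is called for. The marker step is thinly described, but no stated rule is shown to give a wrong result. On the ordinary reading it is a non-inferiority step on the same analysis sets as the composite, run by the cited procedure, with 0.5 SD as the margin that the plan's own rule implies. The most that turns on the unwritten margin is 43–49% of composite-passing trials with any marker verdict changed, or 19–22% per marker, and only between two margins chosen for comparison when there is no true difference. For a marker truly 0.5 SD worse, refusal is about 97% or more either way. These sizes assume unit-SD markers, correlations matched to 2.3029, and a single analysis set. The composite test, its one-sided 2.5% level and the 160 patients are unaffected. Confidence is moderate, because the cited procedure could not be consulted.

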Study Plan of

**A RANDOMIZED, CONTROLLED, DOUBLE-BLIND,
MULTICENTER CLINICAL TRIAL ON HOME PARENTERAL
NUTRITION USING AN OMEGA-3 FATTY ACID ENRICHED
MCT/LCT LIPID EMULSION**

The HOME Study

(HPN WITH OMEGA-3)

STUDY IDENTIFICATION NO.: HC-G-H-1403

NCT03282955

Date of final applicable study plan: 21.05.2021

Marketing Authorization Holder:

**B. Braun Melsungen AG
Germany**

Organized and Financed by:

**B. Braun Melsungen AG
Division Hospital Care
[name]
[name]
Germany**

STUDY OVERVIEW

Title of Study	A randomized, controlled, double-blind, multicenter clinical trial on home parenteral nutrition using an Omega-3 fatty acid enriched MCT/LCT lipid emulsion – The HOME Study (HPN with OMEGA-3)
Investigational Products	
Investigational test product:
 
Lipidem® / Lipoplus® 200 mg/ml (in the following referred as Lipidem)
 
Investigational reference product:
 
Lipofundin® MCT/LCT / Medialipide® 20% (in the following referred as Lipofundin MCT)

Phase	IV
Study Design	Prospective, randomized, controlled, double-blind, multicenter clinical trial performed in two parallel groups
Number of Sites & Countries	Up to 15 sites, planned countries: Poland, Belgium, France, Italy, Netherlands, Spain and United Kingdom
Sample Size	160 patients in total (80 per group)
Indication	Supply of energy, including a readily utilizable lipid component (medium-chain triglycerides) and essential omega-6 fatty acids and omega-3 fatty acids, as part of parenteral nutrition when oral or enteral nutrition is impossible, insufficient or contraindicated.
Primary Objective	Proof of safety and tolerability of home parenteral nutrition (HPN) with an Omega-3 fatty acid enriched MCT/LCT lipid emulsion in adult patients with chronic intestinal failure (CIF) in need of long-term HPN
Primary Variable	The primary endpoint of the study is the change of liver function parameters defined as the sum of the N(0,1)-transformed differences in bilirubin, Alanine transaminase (ALT) and Aspartate transaminase (AST) from baseline to visit 2.
Secondary Objectives	Further safety and efficacy evaluation

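### Safety variables other than the liver composite and its components are compared only by descriptive statistics and tests of difference; reporting differences with 95% confidence intervals would show how much excess harm the data still allow, at almost no cost.

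*Combined protocol and SAP*

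**What the plan says.** The Study Overview gives the primary objective as "Proof of safety and tolerability of home parenteral nutrition (HPN") with the omega-3 enriched emulsion. It lists as secondary safety variables the hepatic tests (including ALP and GGT), blood count and coagulation, other biochemistry (among them triglycerides, cholesterol and CRP), the triene:tetraene ratio and adverse events.

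The section on statistical methods treats these in three ways:

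- **The composite of ALT, AST and bilirubin.** Non-inferiority is concluded when the upper limit of the two-sided 95% confidence interval lies below 1.151.
- **ALT, AST and bilirubin singly.** Once non-inferiority is shown, the composite is broken down to these components at the same level. The text does not say whether a margin applies to them.
- **Everything else.** "Further methods are descriptive statistics including standard procedures for the comparison of two groups", with the t-test, U test and chi-square test in brackets. The Statistical Methods row of the Study Overview says the same. No between-group estimate, confidence interval, margin or expected event rate is named.

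The section on level of significance and power adds: "Tests of secondary variables will be carried out in the area of exploratory data analysis". It states that no multiplicity adjustment will be made.

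**The concern.** For a safety question, the useful result is the largest excess harm that the data have not ruled out. A test of no difference does not supply it. When an event is uncommon and the arms are of modest size, a non-significant result is likely even if the test product doubles the event rate. The plan reasons from a confidence limit for the composite, but does not carry that reasoning over to the other safety data.

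At stake is how the secondary safety tables can be worded. Under an objective of proving safety and tolerability, a table of non-significant p-values invites a stronger statement than it can bear. Nothing in the specified output shows the reader the limit.

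**Working it through.** **Inputs from the documents.** Study Overview: "160 patients in total (80 per group"), and "Patients will be assigned at a 1:1 ratio to receive either Lipidem or Lipofundin MCT". Statistical methods: SD 2.3029 and "mean difference : 1.151 (= non-inferiority margin" δ). Level of significance and power: "The primary endpoint will be tested one-sided with an significance level of" 0.025, and "Sample size calculation is performed with a power of 80"%.

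**Assumptions.** The documents give no adverse event rate and no level for the exploratory tests. I use control rates from 5% to 30% and a two-sided 5% level.

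**Step 1: the plan's own sample size.** The normal approximation gives 2 × (1.960 + 0.842)² × (2.3029 / 1.151)² = 62.8, so 63 per arm. With the noncentral t distribution, power is 79.5% at 63 and 80.1% at 64, so 64 evaluable patients per arm are needed. The documents state no loss rate. A 20% loss would give 64 / 0.80 = 80, the stated number. Both 64 and 80 are carried forward.

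**Step 2: power of the chi-square test for a doubled event rate.** With p̄ the mean of the two rates, the approximation is

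power = Φ{ [ (p₂ − p₁) − 1.96 √(2p̄(1 − p̄)/n) ] / √( [p₁(1 − p₁) + p₂(1 − p₂)]/n ) }.

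For 10% vs 20% and n = 80: 1.96 × √(2 × 0.15 × 0.85 / 80) = 0.1107, and √((0.09 + 0.16)/80) = 0.0559. Then Φ((0.100 − 0.1107)/0.0559) = Φ(−0.19) = 42%. Exact binomial enumeration of the uncorrected chi-square test gives:

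| Control vs test | Power, n = 64 | Power, n = 80 |
|---|---|---|
| 5% vs 10% | 19% | 21% |
| 10% vs 20% | 35% | 42% |
| 15% vs 30% | 53% | 64% |
| 20% vs 40% | 71% | 80% |
| 30% vs 60% | 93% | 97% |

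By the approximation, power for a doubling passes 50% at a control rate of 14.2% (n = 64) or 11.8% (n = 80). A smaller relative increase can be missed at common rates too: 30% vs 45% has 43% / 50% power.

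**Step 3: what an interval would show.** If both arms have the same observed rate p, the 95% half-width of the risk difference is 1.96 √(2p(1 − p)/n). The upper limit of the risk ratio is exp{1.96 √(2(1 − p)/(np))}.

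| Rate in both arms | Half-width, n = 64 / 80 | Upper risk ratio, n = 64 / 80 |
|---|---|---|
| 5% | 7.6 / 6.8 points | 4.5 / 3.9 |
| 10% | 10.4 / 9.3 points | 2.8 / 2.5 |
| 20% | 13.9 / 12.4 points | 2.0 / 1.9 |
| 30% | 15.9 / 14.2 points | 1.7 / 1.6 |

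**Step 4: continuous variables.** The difference detectable with 80% power is 2.80 × √(2/n), which is 0.50 SD at 64 per arm and 0.44 SD at 80.

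**Step 5: an illustration.** Suppose an event occurs in 16 of 80 patients on test and 8 of 80 on reference. Then z = 0.10 / √(2 × 0.15 × 0.85 / 80) = 1.77 and p = 0.077. The Newcombe 95% interval for the risk difference runs from about −1 to +21 points. The test reports non-significance. The interval shows that an excess of about 21 points has not been excluded.

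**The case against.** **The plan does not misuse these tests.** A reader might infer that non-significant secondary tests will be offered as proof of safety. No sentence says so. The tests are declared exploratory, the only decision rule for a safety claim is the confidence limit on the composite, and the stated hypotheses concern deterioration in liver function alone. This stands, and it rules out calling the point an error in inference.

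**A doubling is not missed at every rate.** A reader might also conclude that the trial would usually overlook a doubled adverse event rate. That fails above control rates of about 12-14%. At 30% vs 60% the test succeeds in more than 90% of trials, and the rate of any adverse event need not be low. This stands too.

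**Not every other safety variable is left to generic tests.** ALT, AST and bilirubin have their follow-on step, so they fall outside this point.

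**Intervals add no information, and nothing forbids them.** Tables by arm would let a reader compute them, and the plan foresees a possible SAP update before database lock. It is true that intervals add no power: at a 10% rate the upper risk ratio is still 2.5-2.8. But summaries by arm are not a between-arm estimate, and an exploratory label does not make a p-value show how much harm remains possible. This part of the objection lowers the weight of the point without removing it.

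**The figure of 64 comes from the primary t-test.** Nothing ties it to the denominator for adverse events, so 80 may be the better figure there. The results at 80 lead to the same conclusion.

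**Conclusion.** The point holds as a cheap improvement. For safety variables other than the composite and its three components, the plan names descriptive statistics and tests of difference, and no measure of the excess harm still compatible with the data. This sits poorly with an objective of proving safety and tolerability.

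Its size depends on event rates that the documents do not give. It matters most for less common events, possibly the serious, related or specific ones, and least for frequent ones. The power figures assume a two-sided 5% level, an uncorrected chi-square test and 64 to 80 patients per arm.

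The primary non-inferiority conclusion is not affected.

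**What to change.** In the section on statistical methods and the matching row of the Study Overview, make the test-minus-reference difference with a two-sided 95% confidence interval the main between-group result for these variables:

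- **Laboratory values:** mean difference in change from baseline, or the Hodges-Lehmann estimate where the U test would have been used.
- **Patients with any, serious or related adverse events:** risk difference by a score-type method such as Miettinen-Nurminen or Newcombe.

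Keep any p-values as exploratory. Add two sentences: that p > 0.05 is not evidence of no difference, and that tolerability statements are limited to what the interval excludes on the harmful side.

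The cost is analysis-plan wording and standard SAS output, with no new data. The downside is somewhat more output and wide intervals (about 9-10 points either side at a 10% rate, 14-16 points at 30%), which will make the safety statement less favourable. A doubling of uncommon events still could not be excluded, but the report would show that openly.
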